10.5.3. Efficacy

Spirometry
Predicted FEV₁, Absolute and Percent Reversibility in FEV₁, Percent Predicted FEV₁ and Pre-salbutamol and Post-salbutamol FEV₁/FVC Ratio

 These derived items will be delivered in a dataset from the vendor for central spirometry, except for post-salbutamol FEV₁/FVC ratio, and no recalculation will be performed. Post-salbutamol FEV₁/FVC ratio will be calculated as the ratio of post-salbutamol FEV₁ and FVC values.
Trough

 The trough value for FEV₁, FVC and IC at each of Weeks 4, 12 and 24 is calculated from the values at the assessments made 23 h and 24 h after dosing on the previous day. If the actual time of an assessment is after the time of dosing on the current day, the value for FEV₁, FVC and IC will not be used in the calculation of trough. If one of the values is missing or excluded then the trough will be the single remaining value; otherwise the trough will be the mean of the two values.

BDI/TDI

CCI - This section contained Clinical Outcome Assessment data collection questionnaires or indices, which are protected by third party copyright laws and therefore have been excluded.

SGRQ-C
CCI - This section contained Clinical Outcome Assessment data collection questionnaires or indices, which are protected by third party copyright laws and therefore have been excluded.

CAT
CAT Score

 • The CAT consists of eight items each formatted as a six-point differential scale: 0 (no impact) to 5 (high impact). A CAT score will be calculated by summing the non-missing scores on the eight items. The score can have values ranging from 0 to 40. • If one item is missing, then the score for that item is set as the average of the non-missing items. If more than one item is missing, then the CAT score will be set to missing. • If the language of the CAT conducted at a post-baseline visit is different to the language used at baseline, the CAT score for that visit and all subsequent visits will be set to missing.
CAT Responder

 • A subject will be considered a ‘responder’ according to CAT at each visit if their CAT score has decreased at least 2 units from baseline CAT score. • A subject will be considered a ‘non-responder’ if their CAT score has decreased by less than 2 units, has not changed or has increased compared to baseline. • Missing data will be handled as detailed in Section 10.6.2.

COPD Exacerbations
General

 • The duration of the exacerbation will be calculated as (exacerbation resolution date or date of death - exacerbation onset date + 1). • The time to the first on-treatment exacerbation will be calculated as (exacerbation onset date of first on-treatment exacerbation – date of start of treatment + 1). • For summaries/analyses, subjects will be represented from their Day 1 date to the start date of their first event up to and including their treatment stop date+1 day. • Subjects that have not withdrawn from study treatment or experienced the event are censored

COPD Exacerbations

at their treatment stop date+1 day.
 
 The event rate for exacerbations will be calculated as the total number of events divided by the total annual subject exposure during the time-period of interest
Severity

 Each COPD exacerbation will be categorized based on severity as follows: 
 Mild: no treatment with oral/systemic corticosteroids and/or antibiotics and no hospitalisation Moderate: required treatment with oral/systemic corticosteroids and/or antibiotics (not involving hospitalisation). Severe: required in-patient hospitalization or emergency room Certain displays will include only moderate/severe exacerbations.

Calculation of Daily eDiary Endpoints		
General		

Subjects were instructed to complete the daily eDiary in the evening (typically at bedtime). The parameters collected include rescue use and EXACT-PRO scores.
 
The table below shows which daily eDiary records are used to calculate the daily eDiary parameters for each period. Any diary data collected in the post-treatment phase of the study will not be slotted.
		
Daily Record		Analysis Time Period
Beginning Timepoint (day)	Ending Timepoint (day)	
-28	-1	Week -1 (Baseline)
1	28	Weeks 1 – 4
29	56	Weeks 5 – 8
57	84	Weeks 9 – 12
85	112	Weeks 13 – 16
113	140	Weeks 17 – 20
141	168	Weeks 21 – 24
1	168	Weeks 1 – 24

Note: There is no Day 0. Any records with actual day>168 will not be assigned to a time period. Note: Daily eDiary records that were not assigned to a time period will not be used in calculation of daily eDiary endpoints.
		

 For use of rescue medication endpoint, for a subject to be counted in a time period (except for baseline where at least 14 days non-missing entries required) they must have at least one diary entry recorded for that endpoint during that time period. For E-RS endpoint, for a subject to be counted in a time period they must have at least 16 days non-missing diary entries recorded for that endpoint during that time period. Any daily diary data that were collected post-study treatment discontinuation will be excluded from any analyses, including 4-weekly interval data summaries. 		

Calculation of Daily eDiary Endpoints
Use of Rescue Medication via E-diary

 The mean number of inhalations of rescue use per day and percentage of rescue-free days will be calculated during the 4-weekly interval intervals defined above.
EXACT PRO
EXACT Respiratory Symptoms

 The 4-weekly mean scores for E-RS, and the subscales RS-Breathlessness, RS-Cough and Sputum, and RS-Chest Symptoms will be calculated as the mean of the daily scores in the 4-weekly intervals defined above.
EXACT-RS and Subscale Scores Responder

For each four weekly period;
 
 A subject will be considered as a responder according to E-RS total score if their 4-weekly mean change from baseline EXACT-RS ≤ -2.0. A subject will be considered as a non-responder according to E-RS total score if their 4-weekly mean change from baseline EXACT-RS >-2.0. A subject will be considered as a responder according to RS-Breathlessness score if their 4-weekly mean change from baseline RS-Breathlessness ≤ -1.0. A subject will be considered as a non-responder according to RS-Breathlessness score if their 4-weekly mean change from baseline RS-Breathlessness >-1.0. A subject will be considered as a responder according to RS-Cough & Sputum score if their 4-weekly mean change from baseline RS-Cough & Sputum ≤ -0.70. A subject will be considered as a non-responder according to RS-Cough & Sputum score if their 4-weekly mean change from baseline RS-Cough & Sputum >-0.70. A subject will be considered as a responder according to RS-Chest Symptoms score if their 4-weekly mean change from baseline RS-Chest Symptoms ≤ -0.70. A subject will be considered as a non-responder according to RS-Chest Symptoms score if their 4-weekly mean change from baseline RS-Chest Symptoms >-0.70. Missing data will be handled as outlined in Section 10.6.2.

Rescue use for EMDI

- Will be analysed over Weeks 1 – 24 only
- The Medication Sensor Observation Period for each subject will be defined by the first date of sensor sync and the last date of sensor sync recorded in the database. Since a recorded rescue inhaler usage event in the database is also considered a sync event, if no first sync date is recorded, the date of the first rescue inhaler usage event will be used as the start date of observation. If no last sync date is recorded, the date of the last rescue inhaler usage event will be used as the end date of observation.
- A rescue occasion is defined as an inhaler usage event(s) in which one or more puffs occur within 2 minutes of each other, starting with the first reported puff.
- Days within the Medication Sensor Observation Period with no recorded rescue inhaler usage by the sensor will be assigned a rescue inhaler usage of 0.

Deterioration

- A Clinically Important Deterioration (CID) will be defined by a composite endpoint. A subject is considered to have deteriorated if, in the period from start of treatment to treatment stop + 1 day, one or more of the following occurs (definition dependent);

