
 Time to first on-treatment mild/moderate/severe COPD exacerbation Time to first on-treatment moderate/severe COPD exacerbation Time to first on-treatment severe COPD exacerbation
Model Specification

 A Kaplan-Meier analysis will also be performed for figure showing Kaplan-Meier survivor functions of the proportion of subjects with a first exacerbation over time for each treatment group separately plotted on the same figure.
Model Results Presentation

 Probability of having an event, 95% CI and first quartile time to exacerbation (estimate of the time at which 25% of subjects in each treatment group would have had an exacerbation) Figure showing Kaplan-Meier survivor functions of the proportion of subjects with a first exacerbation over time for each treatment group separately plotted on the same figure.

CID

Secondary Statistical Analysis
Endpoints

 Time to first deterioration of each of the individual components i.e. Trough FEV1, SGRQ total score, CAT score, TDI focal score Time to first CID composite endpoint (SGRQ, FEV1, EXAC (mod/sev)) Time to first CID composite endpoint (CAT, FEV1, EXAC (mod/sev)) Time to first CID composite endpoint (CAT, SGRQ, TDI, EXAC (mod/sev))
Model Specification

 Cox's proportional hazards model, 
Terms in the model:
 
Dependent variable: time to endpoint of interest
 
Categorical: treatment group, stratum (no. of bronchodilators per day during run-in) and geographical region and respective baselines (i.e. endpoint includes CAT and SGRQ then include baselines for these 2 variables) .
 
 Use the 'exact' method for handling ties. (If the analysis will not run using the 'exact' method, then the 'Efron' method for handling ties will be used instead.)
Model Checking & Diagnostics

 The proportional hazards assumption for this method of analysis will be examined by obtaining the Kaplan-Meier estimates of the survival function $S(t)$ over time separately for treatment group. Under the assumption of proportional hazard between the treatment groups, $\ln\{-\ln[S(t)]\}$ for the two groups should be parallel to each other and the distance between them constant. If the curves are approximately parallel, then the proportional hazard assumption is

Secondary Statistical Analysis

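### SAP 10.5.3 grades exacerbation severity by care alone, so a fatal exacerbation without hospital or emergency-room care fits Mild or Moderate and can be missed by the severe endpoint and, if untreated, by the moderate/severe endpoints

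*SAP*

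**What the plan says.** The Severity rule in SAP Section 10.5.3 (COPD Exacerbations) opens with "Each COPD exacerbation will be categorized based on severity as follows" and gives three grades:

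- "Mild: no treatment with oral/systemic corticosteroids and/or antibiotics and no hospitalisation"
- "Moderate: required treatment with oral/systemic corticosteroids and/or antibiotics (not involving hospitalisation", with a closing bracket
- "Severe: required in-patient hospitalization or emergency room"

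None of them mentions outcome. Death appears in that table only as a possible end date in the duration formula: "exacerbation resolution date or date of death - exacerbation onset date + 1".

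The grades feed two secondary endpoints in Section 7.2.1 (items 10 and 11: time to first moderate/severe and time to first severe exacerbation), the moderate/severe rate in Section 7.3.1, and the CID composites in Section 7.2.5.1, such as "Time to first CID composite endpoint (SGRQ, FEV1, EXAC (mod/sev" (brackets close there). Under Section 2.4, once the primary comparison succeeds, each secondary comparison may be declared significant at p below 0.05.

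Two related definitions differ. The exacerbation history in Section 10.5.2 limits severe events to in-patient hospitalisation, with no emergency-room criterion. The Deterioration table in Section 10.5.3 lists an exacerbation of any grade as a CID component.

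**The concern.** A rule based only on care can put the worst outcome in the lowest grade when death comes before care. A subject who dies at home of an untreated exacerbation would count as having a mild event. For the severe and moderate/severe analyses that subject has no event, and follow-up ends at treatment stop plus one day. The only censoring rule given ("Subjects that have not withdrawn from study treatment or experienced the event are censored" at that date) does not mention death. The intercurrent-event strategy in Section 7.1.4, carried to the secondary endpoints by Section 7.2.4, names only discontinuation of treatment.

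The report could then show one event as a fatal SAE in the safety tables and as a mild exacerbation in the efficacy tables. If this is noticed only after unblinding, any regrading would be post hoc.

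**Working it through.** The SAP gives no death rate and no severe-exacerbation rate, so there is no planned figure to reproduce. The check is to apply the rule as written.

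**Step 1. Grade a fatal exacerbation under every combination of care.** Inputs are the three definitions in Section 10.5.3, reading *required* as received.

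| Steroids/antibiotics | In-patient stay | Emergency room | Grades met |
|---|---|---|---|
| no | no | no | Mild |
| yes | no | no | Moderate |
| no | no | yes | Mild and Severe |
| yes | no | yes | Moderate and Severe |
| no | yes | no | Severe |
| no | yes | yes | Severe |
| yes | yes | no | Severe |
| yes | yes | yes | Severe |

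Two of the eight combinations do not reach Severe. Two more meet two grades at once, because Mild and Moderate exclude hospitalisation but not emergency-room care. That overlap does not depend on death.

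**Step 2. Read *required* more broadly.** If a fatal event is taken to have required hospital care that it never received, the first two rows could be called Severe. The first row still meets Mild, which is worded by absence of treatment and hospitalisation, and the second still fits Moderate. The broader reading turns a single wrong grade into two competing grades.

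**Step 3. Trace the endpoints.**

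- *Graded Mild:* counted in time to first mild/moderate/severe and in that rate. Missed by time to first severe, time to first moderate/severe, the moderate/severe rate and the composites in Section 7.2.5.1 that take only moderate/severe exacerbations. Under the Deterioration table in Section 10.5.3, where any exacerbation counts, it would be a CID event.
- *Graded Moderate:* missed by time to first severe only.

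**Step 4. Look for a repair elsewhere.** Table 3.08 (fatal SAEs), Table 2.59 (mortality by Day 30 deterioration status) and Listings 35 and 56 report deaths. None changes an exacerbation grade.

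**Step 5. Sensitivity of the severe endpoint, on assumed rates only.** Randomised subjects per arm: 2424 / 3 = 808 (Section 2.3). Let p be the assumed proportion of an arm with an event graded Severe, and m the assumed number of misgraded fatal events, all in that arm. The share of that arm's severe events that is missed is m / (808p + m).

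| p (assumed) | 808p | m = 1 | m = 3 |
|---|---|---|---|
| 1% | 8.1 | 1/9.1 = 11% | 3/11.1 = 27% |
| 2% | 16.2 | 1/17.2 = 6% | 3/19.2 = 16% |
| 4% | 32.3 | 1/33.3 = 3% | 3/35.3 = 8.5% |

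Putting every such event in one arm is the extreme case. These figures show how sensitive a rare endpoint is; they do not predict what will happen.

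**The case against.** The strongest counter-argument is that this is an ambiguity and may never arise. Severe is defined by what the event required, which leaves room to grade a fatal event as Severe. The protocol, not shown here, may define severity or the recording of fatal events so that an untreated home death is entered only as an SAE; the severity rule would then never be applied to it. Numbers are small, and a subject with an earlier qualifying exacerbation, or for CID an earlier FEV1, SGRQ, CAT or TDI deterioration relevant to the composite, is unaffected.

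Much of this stands and limits the point. It does not remove it: Section 10.5.3 writes out a complete rule without deferring to the protocol, that rule is what will be programmed, and the broader reading leaves two grades in force.

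A reader might infer more than the SAP supports:

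- *That the plan expressly foresees exacerbations that cause death.* The duration formula, ending at "exacerbation resolution date or date of death", shows only that death can close an exacerbation record. The cause could be anything.
- *That every such event is certainly misgraded and drops out of all the exacerbation endpoints.* A Moderate grade costs one endpoint. A Mild grade leaves the event in the all-severity endpoints, and for CID the SAP's own sections disagree.
- *That a particular number of subjects will be affected or the severe hazard ratio will visibly shift.* This needs mortality and place-of-death rates that the SAP does not give, and nothing in it suggests a difference between arms.

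**Conclusion.** The point holds in a limited form. As written, a fatal exacerbation without in-patient or emergency-room care meets Mild or Moderate, and Severe is at best a competing reading. The severe endpoint can miss both kinds; the moderate/severe endpoints, and the composites restricted to that class, can miss only the untreated kind.

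The number affected cannot be derived from the document and is probably very small. The primary endpoint is not affected, and deaths remain visible in the safety displays. It still merits correction because time to first severe and time to first moderate/severe are secondary endpoints open to inference under Section 2.4, and a rare endpoint is sensitive to a few events. The conclusion assumes that a fatal exacerbation outside hospital would be recorded as an exacerbation at all, and that the protocol has no overriding definition.

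**What to change.** Before unblinding, amend the Severity rule in SAP Section 10.5.3 so that, for analysis, an exacerbation with on-treatment onset that the investigator records as having a fatal outcome is classified as Severe whatever care was given. Apply this in the time-to-first, rate and CID derivations.

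In the same edit:

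1. Make the three grades mutually exclusive by stating the single grade that an emergency-room-only event receives.
2. Reconcile the Severe definition in Section 10.5.3 with the one used for exacerbation history in Section 10.5.2.
3. Reconcile the exacerbation component in the Deterioration table of Section 10.5.3 (any exacerbation) with the composites in Section 7.2.5.1 (moderate/severe only).

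The cost is a few lines of text and one extra programming condition; date of death is already an input to the duration derivation. There is a small downside: the rule relies on the recorded link between exacerbation and death, and it must be checked against the protocol definition so that the two do not diverge. It changes an analysis classification only, not patient management.

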10. APPENDICES

10.1. Appendix 1: Schedule of Activities

10.1.1. Protocol Defined Schedule of Events

			Blinded Treatment					
Visit	Pre-screen ¹ 0	Screen/ Run-in 1	Rando- mization 2	3	4	5	EW Visit ²	Telephone Follow up contact 6
Week	-10 to -4	-4	0	4	12	24		
Day	-70 to -28	-28	1	28	84	168		7 days after V5 or EW Visit
Window	-7/+2 days	-7/+2 days	-7/+2 days	-7/+2 days	-7/+2 days	-7/+2 days		±3 days
Screen/Baseline								
Informed consent	X							
Demography	X							
Medical/COPD history		X						
Smoking history/status		X						
Smoking cessation counselling		X						
Concomitant medication assessment	X	X	X	X	X	X	X	X
Height and weight		X						
Cardiovascular History/family history of premature CV disease)		X						
Screening spirometry (including post bronchodilator testing) ³		X						
CAT questionnaire		X	X					
Verify Inclusion/Exclusion Criteria		X						
Training on use of inhalers		X	X					
Training on use of eDiary and eMDI		X	X					
Verify randomization Criteria			X					

			Blinded Treatment					
Visit	Pre-screen ¹ 0	Screen/ Run-in 1	Rando- mization 2	3	4	5	EW Visit ²	Telephone Follow up contact 6
Week	-10 to -4	-4	0	4	12	24		
Day	-70 to -28	-28	1	28	84	168		7 days after V5 or EW Visit
Window	-7/+2 days	-7/+2 days	-7/+2 days	-7/+2 days	-7/+2 days	-7/+2 days		±3 days
Register Visit in InForm	X	X	X	X	X	X	X	X
Register Visit in RAMOS NG	X	X	X	X	X	X	X	X
Efficacy/HRQoL assessments								
Spirometry, including pre-dose FEV ₁ , trough FEV ₁ and inspiratory capacity			X	X	X	X		
SAC BDI questionnaire ⁴			X					
SAC TDI questionnaire ⁴				X	X	X		
SGRQ-C questionnaire ⁴			X	X	X	X		
CAT questionnaire ⁴		X	X	X	X	X		
EXACT/ER-S: COPD ⁵		—————→						
Patient Global Rating of COPD severity			X	X	X	X		
Patient Global Rating of Change in COPD				X	X	X		
Safety assessments								
Adverse events/Serious adverse events ⁶	X	X	X	X	X	X	X	X
COPD exacerbation assessment	X	X	X	X	X	X	X	X
12-Lead ECG		X						
Urine pregnancy test ⁷		X	X			X	X	
Pharmacogenetic sample ⁸			←———— X —————→					
Medication/Supplies								
Dispense rescue albuterol/slabutamol. Dispense MDI ⁹		X	X	X	X	X		
Assess COPD medication compliance ¹⁰ during run-in			X					
Dispense eDiary		X						
Assess compliance with eDiary during run-in			X					
Collect rescue albuterol/slabutamol.			X	X	X	X	X	

			Blinded Treatment					
Visit	Pre-screen ¹ 0	Screen/ Run-in 1	Rando- mization 2	3	4	5	EW Visit ²	Telephone Follow up contact 6
Week	-10 to -4	-4	0	4	12	24		

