Day	-70 to -28	-28	1	28	84	168		7 days after V5 or EW Visit
Window	-7/+2 days	-7/+2 days	-7/+2 days	-7/+2 days	-7/+2 days	-7/+2 days		±3 days
Collect eDiary						X	X	
Dispense study treatment ¹¹			X	X	X			
Collect study treatment				X	X	X	X	
Assess study treatment compliance during treatment ¹⁰				X	X	X	X	
Study sub-set								
Physical activity monitor ¹²		X	X	X		X		
Collect Physical activity monitor						X	X	

1. Pre-screen Visit 0 must be completed prior to Screening Visit1. It can be completed 6 weeks prior or on the same day of V1, if no wash out of exclusionary medications is required.
2. Early Withdrawal Visit: Subjects that withdraw should return to the clinic as soon as possible to complete the Early Withdrawal Visit procedures.
3. Spirometry at screening should be performed as described in (Section 7.2.2.1 in the protocol).
4. SAC BDI, SAC TDI, SGRQ-C, CAT questionnaires will be completed at clinic visits and in the eDiary
5. EXACT/ER-S: COPD is completed daily in the eDiary approximately 2 hours before bed-time, starting on Day 1 of the run-in period.
6. For the start date of collecting AEs and SAEs see (Appendix 4)
7. Pregnancy test: for females for child bearing potential only.
8. Pharmacogenetic sample may be drawn at visit 2 or any visit after.
9. Rescue medication use to be recorded in the eDiary daily **and** in some sites in the eDiary and the eMDI
10. Sites are requested to call subjects every 2 weeks to remind them to take study treatment regularly and to record the time of the morning and evening dose in the eDiary.
11. In order to ensure subjects have sufficient doses of study treatment, they must return to clinic within 30 days from V2 and within 60 days from V3 respectively.
12. The Actigraph GT9X should be worn for 7 days from Visit 1, for 7 days from Visit 2, for 7 days from Visit 3 and for 7 days prior to Visit 5.

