10.6.2.3. Handling of Missing Data for Statistical Analysis

Element	Reporting Detail
Responder	
 • Subjects with a missing baseline will have responder status as missing • Subjects with missing post-baseline data at a time point and a subsequent non-missing assessment will not be considered a responder or non-responder but will be left as missing at that time point • Subjects with a missing post-baseline assessment with no subsequent non-missing assessments will be considered a non-responder for that and all subsequent time points. • Subjects with a baseline but all missing post-baseline data will be considered a non-responder at all time points.

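### The 16-entry E-RS minimum is not scaled in Weeks 21-24, so subjects seen early in the Visit 5 window face a stricter rule and can be scored non-responders because of visit timing

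*SAP*

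**What the plan says.** - **Period.** The eDiary table in SAP 10.5.3 fixes the last 4-weekly period by study day ("141 168 Weeks 21 – 24"). It cannot be extended to the right: "Any records with actual day>168 will not be assigned to a time period". Diary data collected after treatment has stopped are also excluded.
- **Minimum.** The rule for E-RS is "For E-RS endpoint, for a subject to be counted in a time period they must have at least 16 days non-missing diary entries". The count does not depend on how many evenings were available. Rescue use, from the same diary, needs only one entry per on-treatment period.
- **Visit timing.** In SAP 10.1.1, Visit 5 is at nominal Day 168 with a window of -7/+2 days, that is, Days 161-170. The row "Collect eDiary" is marked at Visit 5 and at the early withdrawal visit. The footnote on the instrument says "EXACT/ER-S: COPD is completed daily in the eDiary approximately 2 hours before bed-time".
- **Missing values.** SAP 10.5.3 refers missing E-RS responder data to 10.6.2. There: "Subjects with a missing post-baseline assessment with no subsequent non-missing assessments will be considered a non-responder for that and all subsequent time points". An earlier gap that is followed by a later value is left as missing.
- **Analyses affected.** SAP 7.2.5.1 analyses the E-RS total and three subscale scores by 4-weekly period, both as means (repeated-measures model) and as responder proportions (generalized linear mixed model).

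**The concern.** These rules are reasonable one by one but do not fit together in the last period. In Weeks 1-20 a subject who stays on treatment always has 28 evenings in each period. In Weeks 21-24 the number of evenings depends on the date of Visit 5, and eight of the ten permitted days (161-168) leave fewer than 28. The minimum does not move with it.

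Weeks 21-24 is also the one period with no later value, so every shortfall there becomes a non-response. The same shortfall in Weeks 17-20, followed by a counted Weeks 21-24, would simply be missing. A subject's recorded response could therefore change because a visit was booked a week early, with no change in symptoms or diary habits. At stake are the final-period results of the four E-RS responder endpoints and, to a lesser degree, the final-period means. A drop in responder proportions from Weeks 17-20 to Weeks 21-24 could be read as waning effect when part of it comes from scheduling.

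**Working it through.** **Inputs from the SAP.** Last period Days 141-168; minimum 16 entries (10.5.3). Visit 5 on Days 161-170; evening entry; diary collected at Visit 5 (10.1.1). From the last two it follows that the last possible entry is the evening before Visit 5.

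**Inputs not in the SAP (assumptions).** Daily completion probability *p* (0.75 to 0.90 shown), days independent, and the spread of Visit 5 dates.

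**Step 1: evenings available and share required.** With Visit 5 on Day *d*, n = min(d - 1, 168) - 140, and the required share is 16/n. A full period gives 16/28 = 57.1%, with 12 missed evenings allowed.

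| Visit 5 day | n | 16/n | Misses allowed |
|---|---|---|---|
| 161 | 20 | 80.0% | 4 |
| 162 | 21 | 76.2% | 5 |
| 163 | 22 | 72.7% | 6 |
| 164 | 23 | 69.6% | 7 |
| 165 | 24 | 66.7% | 8 |
| 166 | 25 | 64.0% | 9 |
| 167 | 26 | 61.5% | 10 |
| 168 | 27 | 59.3% | 11 |
| 169-170 | 28 | 57.1% | 12 |

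**Step 2: one subject.** At a steady 75% completion, Weeks 17-20 give 0.75 × 28 = 21 entries, which is counted. With Visit 5 on Day 161, Weeks 21-24 give 0.75 × 20 = 15 entries, which is not counted. The subject is missing in the repeated-measures model and a non-responder in the responder model.

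**Step 3: chance of not being counted**, P(Binomial(n, p) ≤ 15). The last column averages over Days 161-170 with equal weight.

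| p | Full 28 days | Day 168 | Day 165 | Day 161 | Even spread |
|---|---|---|---|---|---|
| 0.75 | 1.1% | 2.2% | 12.1% | 58.5% | 17.9% |
| 0.80 | 0.15% | 0.35% | 3.6% | 37.0% | 8.7% |
| 0.85 | 0.01% | 0.02% | 0.6% | 17.0% | 3.1% |
| 0.90 | <0.01% | <0.01% | 0.03% | 4.3% | 0.6% |

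**Step 4: completion that differs between subjects.** Step 3 gives every subject the same *p*. With beta-binomial completion (a + b = 10, an assumption), the loss is:
- mean 0.80: 6.2% in a full period, 37.5% on Day 161, 16.6% with even spread;
- mean 0.90: 1.1%, 13.1% and 4.5%.

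The ratio between the final and a full period shrinks, but the average excess does not vanish: 16.6 - 6.2 = 10.4 percentage points, and 4.5 - 1.1 = 3.4.

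**Step 5: effect on the odds ratio.** Take true responder proportions of 40% and 33% (assumption): OR = (0.40/0.60)/(0.33/0.67) = 1.354. Turn 8.7% of responders in each arm into non-responders: 0.40 × 0.913 = 0.365 and 0.33 × 0.913 = 0.301, so OR = 1.334. At 45% and 35% the OR moves from 1.519 to 1.485. The proportions fall by about 3 to 4 percentage points; the odds ratios move little.

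**The case against.** The strongest reply is that this is an edge effect. At the nominal Day 168 the requirement is 59% against 57%, and from Day 169 nothing changes. A subject who fills in the diary every evening is always counted, even on Day 161; to be lost there, at least 5 of 20 evenings must have been missed. The average loss rests on two quantities the SAP does not give. For the means, the repeated-measures model under missing at random still uses periods one to five, so little is lost. Sixteen days is also the E-RS baseline minimum in SAP 5.2, so a fixed count keeps both sides of every change score on at least 16 days. And E-RS is defined over 24 weeks; no section makes Weeks 21-24 its decision point.

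All of this stands as a limit on size. It does not remove the mismatch: a subject on treatment and seen inside the window can still be scored a non-responder for a reason unrelated to symptoms. Elsewhere the SAP allows for visit timing. Section 10.2.1 keeps early clinic values at their nominal visit, and 10.5.3 ties the last activity-monitor week to the days before Visit 5.

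A reader might infer that the last period is far stricter for everyone, or that fully compliant completers are discarded. The first holds only early in the window. The second cannot be established: the SAP sets no on-treatment diary-completion standard, so compliance can be judged only on visit timing. A reader might also infer a bias between arms. The rule and window are the same in all arms, so nothing in the documents supports that.

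**Conclusion.** The point holds in limited form. The required completion in Weeks 21-24 runs from 80% for a Day 161 visit down to 57% for Days 169-170, against 57% in the other on-treatment periods, and 10.6.2.3 turns every final-period shortfall into a non-response. The day arithmetic rests on the SAP alone, plus the inference that no entry is made after the diary is handed back.

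The number of subjects affected is not known. Under independent days and evenly spread visits it averages from about 18% at 75% completion down to 0.6% at 90%. It falls towards the Day 168 figures (2.2% or less) if visits cluster there, and rises if completion varies between subjects. The consequence is lower final-period responder proportions in all arms, slight dilution of the odds ratios and some lost final-period means. The primary trough FEV1 analysis is unaffected. The correction is worth making because it is nearly free, not because the trial's conclusions depend on it.

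**What to change.** In SAP 10.5.3, keep the last period at Days 141-168. For subjects who complete Visit 5 on treatment, replace the flat 16 entries in that period by at least 16/28 (57%) of the evenings available before Visit 5, rounded up. That is 12 of 20 for Day 161, 14 of 24 for Day 165 and 16 of 27 for Day 168. Apply it to the total and subscale scores, in both the mean and responder analyses. Leave the other periods, and subjects who stop treatment early, as they are.

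With *p* = 0.80, the Day 161 loss falls from 37.0% to 1.0% and the even-spread average from 8.7% to 0.5%. At *p* = 0.75 the average falls from 17.9% to 2.4%.

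The cost is one sentence and a small programming change before unblinding. The downside is that some final-period means will rest on 12 to 15 days instead of at least 16. Sliding the period to the 28 days before Visit 5 is not advised: for a Day 161 visit it would use Days 133-160, so Days 133-140 would count in two repeated-measures periods.
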